1.2 Cancer Peptide Vaccine

The cancer peptide vaccine elicits its effect through the cytotoxic T lymphocyte (CTL) induction. The administered epitope peptides are taken up into dendritic cells, which are an antigen presentation cell, and then CTL induction specific to tumor antigen is triggered through the recognition by CTL of the epitope peptide/major histocompatibility complex (MHC) class I on the surface of the cells. In humans, MHC class I is called human leukocytes antigen (HLA) class I. The induced CTL shows cytotoxic activity against target tumor cells of which the epitope peptide/MHC class I is expressed on the surface.

1.3 Clinical Development of S-588410

To date, Shionogi & Co., Ltd. has developed 2 cancer peptide vaccines including the HLA-A*24:02 restricted epitope peptides. These are S-288310 (comprising 2 peptides of S-288301 and S-288302) and S-488410 (comprising 3 peptides of S-488401, S-488402, and S-488403). These peptides are shown as follows:

- S-288301 (DEP domain containing 1 [DEPDC1]-derived peptide)
- S-288302 (M-phase phosphoprotein 1 [MPHOSPH1]-derived peptide)
- S-488401 (up-regulated lung cancer 10, [URLC10]-derived peptide)
- S-488402 (cell division cycle associated 1 [CDCA1]-derived peptide)
- S-488403 (KH domain-containing protein overexpressed in cancer 1 [KOC1]-derived peptide)

Clinical studies of S-288310 have been conducted in patients with bladder cancer since DEPDC1 and MPHOSPH1 were originally found to be expressed in bladder cancer. DEPDC1 and MPHOSPH1 were also found in the upper urothelial carcinoma, and an investigator-initiated translational research study is being conducted in patients with advanced upper urinary tract carcinoma [8]. Clinical studies of S-488410 have been conducted in patients with esophageal cancer or lung cancer since URLC10, CDCA1, and KOC1 were originally found to be expressed in esophageal cancer and lung cancer cells.

Although S-588410 has not been studied in human, the safety and the immunogenicity of these 5 peptides has been already evaluated in these clinical studies of S-288310 or S-488410 (refer to the current investigator's brochure [IB] for detail).

Tumor heterogeneity, tumor immune escape, and difference in immune response (CTL response) to each peptide among patients have been recently recognized through previous development of cancer peptide vaccine and a multi-peptide vaccine increases the likelihood of inducing an immune response [9, 10]. Tumor heterogeneity means the difference among patients or tumor cells in antigen expression pattern. Therefore, cancer peptide vaccines including many types of antigen-derived peptide are expected to be highly effective in a wider patient population. All of the 5 antigens have recently been demonstrated to be expressed at high levels on cancer tissues of urinary bladder cancer, esophageal cancer, gastroesophageal cancer, and head and neck cancer tissues (refer to Section 4.1.2 in the current IB for S-588410). Based on these recent findings, the future clinical development will be planned as the HLA-A*24:02 restricted 5-peptide vaccine, S-588410, which includes the five individual peptide of S-288301, S-288302, S-488401, S-488402, and S-488403.

After completion of first-line chemotherapy, maintenance therapy for cancer may prolong the time of progression and result in improvement of overall survival. Maintenance therapy for cancer has already been conducted in clinical studies of some drugs [11, 12, 13], however, none have been approved yet. As a cancer peptide vaccine is expected to have fewer side effects, S-588410 is expected to meet the unmet medical needs of maintenance therapy for patients with advanced and/or metastatic bladder cancer, whose disease responds or remains stable after completion of first-line chemotherapy. Therefore, this open-label, multicenter study with S-588410 as maintenance therapy will be conducted in patients with advanced and/or metastatic bladder cancer whose disease is in complete response (CR), partial response (PR), or stable disease (SD) after completion of first-line chemotherapy as an early phase study (prior to conduct of a large-scale study).

2. STUDY OBJECTIVES

2.1 Primary Objective

The primary objective of this study is:

- To evaluate the CTL induction in HLA-A*24:02-positive patients receiving S-588410 for 12 weeks.

2.2 Secondary Objectives

The secondary objectives of this study are:

- To evaluate the specific CTL induction over time in HLA-A*24:02-positive patients receiving S-588410 for 1 year.
- To estimate antitumor effect in HLA-A*24:02-positive patients receiving S-588410.
- To estimate progression-free survival (PFS) in HLA-A*24:02-positive patients receiving S-588410.
- To estimate overall survival (OS) in HLA-A*24:02-positive patients receiving S-588410.
- To evaluate the safety and tolerability in patients receiving S-588410.
- To assess the general health status in terms of European Organization for Research and Treatment of Cancer (EORTC) QLQ-C30 and Euro-QOL 5 dimension 5 level version (EQ-5D-5L) in HLA-A*24:02-positive patients receiving S-588410.
- To collect data of tumor evaluation, PFS, OS, and EORTC QLQ-C30 and EQ-5D-5L questionnaires in HLA-A*24:02-negative patients without the study treatment.

3. INVESTIGATIONAL PLAN

3.1 Overall Study Design and Plan

The study is an open-label, multicenter study and consists of 2 study periods:

- The Screening Period is 28 days prior to enrollment. Potential patients who provided written informed consent will be screened for assessment of the eligibility in the screening period.
- The Treatment Period/Observation Period is 24 months (104 weeks) after enrollment. Eligible patients will be enrolled in the study, and assigned to S-588410 Group or Observation Group depending on the HLA-A genotype. Enrollment form will be reported via FAX.

[figure not shown]
For Japanese study sites	Sponsor's study manager: [REDACTED], Clinical Research Department, Shionogi & Co., Ltd. FAX: [REDACTED]
For EU study sites	Sponsor's medical monitor: [REDACTED] Medical Consultant Oncology, Shionogi Ltd. Fax: [REDACTED]

- HLA-A*24:02-positive patients will be enrolled in the S-588410 Group. Each patient will receive 1 mL of S-588410 emulsion, which contains 1 mg each of S-288301 (DEPDC1-derived peptide), S-288302 (MPHOSPH1-derived peptide), S-488401 (URLC10-derived peptide), S-488402 (CDCA1-derived peptide), and S-488403 (KOC1-derived peptide). S-588410 will be injected subcutaneously in the patient's inguinal, axillary, or cervical region once weekly for 12 weeks and once every 2 weeks thereafter for up to 24 months. They will undergo efficacy assessments (specific CTL measurement, anti-tumor evaluation, PFS, OS, and EORTC QLQ-C30 and EQ-5D-5L questionnaire assessment), safety assessments (injection site assessment, physical examination, vital sign assessment, electrocardiogram [ECG], Eastern Cooperative Oncology Group Performance Status [ECOG PS], laboratory tests, and adverse event [AE] monitoring), and other assessments (antigen expression testing and T-cell receptor repertoire analysis).
- HLA-A*24:02-negative patients will be enrolled in the Observation Group and will not receive the study drug. They will undergo the efficacy and safety assessments similarly to the S-588410 Group except for specific CTL measurement, and injection site assessment, and T-cell receptor repertoire analysis.

Follow-up assessments will be performed in all enrolled patients for 3 years after enrollment of the last patient. The following data will be reported to the sponsor: survival or death, date and site of progression, and date, description of, and response to subsequent therapy for the target disease (ie, bladder cancer).

The study design is shown in [Figure 3-1](#). The study events table is shown in [Appendix 1](#) and [Appendix 2](#).

Figure 3-1 Study Schematic

3.2 Rationale for Study Design

3.2.1 Rationale for the patient population

The patient population eligible for this study was selected based on the following reasons:

- As stated in the Food and Drug Administration (FDA) Guidance for Industry “Clinical considerations for therapeutic cancer vaccines October 2011” [14], patients with no evidence of residual diseases or minimal burden of disease may provide adequate time for the cancer vaccine to elicit a detectable immune response.
- Platinum-containing chemotherapy is recommended as the standard first-line chemotherapy in all regions of US and Europe, and Japan (GC or MVAC as the main choice) [3, 4, 5].
- For the majority of the patients, the disease will continue to progress even after completion of the first-line chemotherapy, as evidenced by the poor 5-year survival data.
- There are currently no treatments approved for maintenance therapy following first-line platinum containing chemotherapy in this patient population.
- Maintenance therapy (in patients after first-line chemotherapy including patients whose disease responds or remain stable) has been reported in several clinical studies [11, 12, 13].

3.2.2 Rationale for dosage of S-588410

The previous phase 1/2 studies of S-288310 (Study 0920P1611) and S-488410 (Study 1008P1711) suggested that there is no dose-relationship between the CTL induction and the tested doses (1 to 4 mg) and that the local symptoms at injection sites may be caused by adjuvant (Montanide ISA 51 VG). Since lower volume of subcutaneous injection is considered more tolerable for patients, 1 mg of S-588410 is selected as optimal dose for the

CTL induction.

As for duration of treatment, 24-months was selected as the appropriate duration since 24-months is approximately twice the duration of the reported median overall survival (10.3 months) [11] in bladder cancer patients after the first-line chemotherapy.

The dosing frequency was chosen based on the Study 0920P1611 and the Study 1008P1711 since the CTL induction within 12 weeks is already shown well at weekly injection and efficacy and safety are confirmed at weekly or every 2 weeks injection thereafter in the studies. Therefore the dosing frequency of S-588410 is chosen as weekly injection for 12 weeks, followed by every 2 weeks thereafter.

The method of administration is also selected based on the Study 0920P1611 and Study 1008P1711.

3.3 Study Duration

3.3.1 Study Duration in individual patients

The total study duration will be 108 weeks (Screening Period, 4 weeks; Treatment Period, 104 weeks).

3.3.2 Planned Study Duration for the Study

The planned study duration is from February 2014 to October 2018.

4. STUDY POPULATION SELECTION

4.1 Study Population

Male or female patients 20 years of age or older, with advanced and/or metastatic bladder cancer who satisfy the following eligibility criteria will be enrolled.

4.2 Inclusion Criteria

Patients who fulfill all of the following criteria assessed by the end of screening period will be included in the study.

1. Patients with advanced and/or metastatic bladder cancer (including urothelial cancer of renal pelvis, ureters, and urethra) who have CR, PR, or SD based on the Response Evaluation Criteria in Solid Tumors (RECIST) version 1.1 at the end of at least 4 cycles of first-line platinum-containing systemic chemotherapy.
(Note: Patients who have subsequently received another platinum-containing chemotherapy due to intolerance* of first-line platinum-containing chemotherapy are eligible if the total number of cycles of platinum-containing regimens reached 4 cycles or more. The patients had no PD at the time of change of platinum-containing chemotherapy. *: any non-hematologic toxicity with grade 3 or higher, or hematologic toxicity with grade 4, according to Common Terminology Criteria for Adverse Events [CTCAE] version 4.03.)
2. Patients who are male or female aged ≥ 20 years at the time of informed consent.
3. Patients with the ECOG PS 0 or 1 at enrollment.
4. Patients who have a lymphocyte count accounting for 15% or higher of the total white blood cell count within 28 days before enrollment.
5. Patients who are willing and able to provide formalin-fixed and paraffin-embedded bladder cancer tissues for antigen expression measurement.
6. Patients who provide a personally signed and dated informed consent document for participation in the study.

4.3 Exclusion Criteria

Patients who meet any of the following criteria by the end of screening period will be excluded from the study.

1. Patients who have progressive disease (PD) on RECIST version 1.1 at the end of at least 4 cycles of first-line platinum-containing chemotherapy.
2. Patients who are judged to have clinically progressive symptoms at the end of at least 4 cycles of first-line platinum-containing chemotherapy by the investigator or subinvestigator.
3. (deleted)
4. Patients with a history of malignant cancer (except for carcinoma in situ or intra-mucosal cancer that resolved with endoscopic therapy) within 5 years before enrollment.
5. Patients who received any prior therapies for target disease within 3 weeks before the first administration of S-588410.
6. Patients who cannot receive the first administration of S-588410 within 12 weeks

-
- after the last administration of chemotherapy.
7. Patients who are expected to require any of the following therapies between enrollment and completion or discontinuation of the study treatment.
 - Anti-malignant tumor drug
 - Systemic corticosteroid (except for corticosteroid defined as the equivalent of prednisone ≤ 10 mg/day orally)
 - Systemic immunosuppressant drug
 - Immunotherapy
 - Radiotherapy (except for restricted radiotherapy for pain relief of bone metastasis) for the target disease
 - Surgical therapy for the target disease
 - Hyperthermia for the target disease
 - Herbal medicine with anti-tumor or immunosuppressant effect
 - Other investigational new products
 8. Patients who have severe (CTCAE version 4.03 grade 3 or higher) concurrent hepatic impairment, renal impairment, heart disease, hematological disease, respiratory disease, or metabolic disease, with the exception of any symptoms and/or signs associated with target disease.
 9. Patients who have the following laboratory data with grade 3 or higher according to CTCAE version 4.03 criteria within 28 days before enrollment.
 - White blood cell count $<2000/\text{mm}^3$ or $>100\,000/\text{mm}^3$
 - Platelet count $<50\,000/\text{mm}^3$
 - Hemoglobin <8.0 g/dL
 - Aspartate aminotransferase (AST) or alanine aminotransferase (ALT) $>5.0 \times$ the upper limit of normal (ULN)
 - Total bilirubin $>3.0 \times$ ULN
 - Serum creatinine $>3.0 \times$ ULN
 10. Patients who has an increase in an eosinophil counts (more than $5000/\text{mm}^3$), within 28 days before enrollment, or patients with a history or current complication of eosinophilic pneumonia or interstitial pneumonia. If patients have symptoms and signs suggestive of pneumonia before enrolment, the investigator or subinvestigator must confirm the presence or absence of concurrent eosinophilic pneumonia or interstitial pneumonia on the basis of additional examinations such as chest x-ray.
 11. Patients who have known human immunodeficiency virus infection.
 12. Patients with uncontrolled systemic or active infection.
 13. Patients who had any diseases with the risk of sudden death within 12 months before enrollment.
 - [Examples]
 - Myocardial infarction
 - Unstable angina
 - Coronary or peripheral artery bypass graft surgery
 - Thrombotic or embolic events such as pulmonary embolism, deep vein thrombosis, or transient ischemic attack
 14. Patients who have known brain metastases.
 15. Patients with a history or evidence of autoimmune diseases and/or immunodeficiency disorders.

[Examples]

- Systemic lupus erythematosus
 - Multiple sclerosis
 - Systemic sclerosis
 - Rheumatoid arthritis
16. Patients with a history of severe (CTCAE version 4.03 grade 3 or higher) allergic reaction to a drug, vaccination, or biological preparation.
 17. Patients who are hospitalized for treatment at enrollment.
 18. Female patients who are lactating or pregnant. Female patients who are of childbearing potential, not included in any of the following, are positive for the pregnancy test at enrollment.
 - Postmenopausal woman (at least 2 years since their last regular menstrual period without any other medical reason)
 - Women who are surgically sterile by hysterectomy and/or bilateral oophorectomy, or by tubal ligation
 19. Patients who cannot or do not intend to practice effective contraception (barrier contraceptives [male condom, female condom, or diaphragm with a spermicidal gel]; hormonal contraceptives [implants, injectables, combination oral contraceptives, or transdermal patches]; or intrauterine devices) as per physicians' recommendations from enrollment to 90 days after completion or discontinuation of study treatment.
 20. Patients who received DEPDC1, MPHOSPH1, URLC10, CDCA1, or KOC1 peptide vaccines before.
 21. Patients who received any other investigational products within 28 days or 5 half-lives of the investigational products before enrollment whichever is longer.
 22. Patients who are considered ineligible for this study by the investigator or subinvestigator due to any reasons, including inability to understand and follow the requirements of the study.

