 13. Patients who had any diseases with the risk of sudden death within 12 months before enrollment.
 - [Examples]
 - Myocardial infarction

- Unstable angina
 - Coronary or peripheral artery bypass graft surgery
 - Thrombotic or embolic events such as pulmonary embolism, deep vein thrombosis, or transient ischemic attack
14. Patients who have known brain metastases.
15. Patients with a history or evidence of autoimmune diseases and/or immunodeficiency disorders.

[Examples]

- Systemic lupus erythematosus
 - Multiple sclerosis
 - Systemic sclerosis
 - Rheumatoid arthritis
16. Patients with a history of severe (CTCAE version 4.03 grade 3 or higher) allergic reaction to a drug, vaccination, or biological preparation.
17. Patients who are hospitalized for treatment at enrollment.
18. Female patients who are lactating or pregnant. Female patients who are of childbearing potential, not included in any of the following, are positive for the pregnancy test at enrollment.
- Postmenopausal woman (at least 2 years since their last regular menstrual period without any other medical reason)
 - Women who are surgically sterile by hysterectomy and/or bilateral oophorectomy, or by tubal ligation
19. Patients who cannot or do not intend to practice effective contraception (barrier contraceptives [male condom, female condom, or diaphragm with a spermicidal gel]; hormonal contraceptives [implants, injectables, combination oral contraceptives, or transdermal patches]; or intrauterine devices) as per physicians' recommendations from enrollment to 90 days after completion or discontinuation of study treatment.
20. Patients who received DEPDC1, MPHOSPH1, URLC10, CDCA1, or KOC1 peptide vaccines before.
21. Patients who received any other investigational products within 28 days or 5 half-lives of the investigational products before enrollment whichever is longer.
22. Patients who are considered ineligible for this study by the investigator or subinvestigator due to any reasons, including inability to understand and follow the requirements of the study.

Sample size:

The sample size of the S-588410 Group is 42 patients. The sample size of the Observation Group may be up to 42 patients.

Test Drug, Dose, and Mode of Administration:

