7.2 Baseline Information

7.2.1 Baseline Patient Characteristic and Medical History

The following baseline patient characteristics and medical history will be obtained at the initiation of the study and entered in the CRF:

- Baseline patient characteristics
 - Date of enrollment, date of patient's written informed consent, date of birth, sex, ethnicity, and race
 - TNM Clinical Classification (T, primary tumor; N, regional lymph nodes; M, distant metastasis)^{*1} at enrollment in the study
- Medical history
 - Information related to the target disease^{*1} (at the time of definitive diagnosis): Primary lesion, date of definitive diagnosis, TNM Clinical Classification^{*1}, histology, G histopathological grading
 - Surgical history for the target disease (see Section 6.1.1)
 - Previous disease other than the target disease (cancer or conditions that required hospitalization within 1 year before enrollment), and complication (with exception of any symptoms and/or signs associated with target disease)
 - Prior therapy for the target disease and other than the target disease (see Section 6.1)

*1: In accordance with TNM Classification of Malignant Tumours 7th Edition by UICC (Union for International Cancer Control).

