7.4.6.2 Pregnancy Tests

Pregnancy test will be performed only for female patients with the exception of patients who are postmenopausal (at least 2 years since their last regular menstrual period without any other medical reason) or are surgically sterile by hysterectomy and/or bilateral oophorectomy, or by tubal ligation. Urine or serum pregnancy test will be performed at screening in both the S-588410 and the Observation Groups, and Visit 59 (or Discontinuation) in the S-588410 Group.

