7.9 Acceptable Time Window

All assessments will be performed according to the schedule as shown in [Appendix 1](#) and [Appendix 2](#). The following acceptable time window, as shown in [Table 7-3](#), can be accepted even if the timing of the measurement departs from the schedule specified in [Appendix 1](#) and [Appendix 2](#). Data departed from this time window will be handled as missing data for the study visit. However, skipping of Visit may be allowed from Visit 14 through Visit 58, as long as they are not two or more successive skips or skipping of the following Visits for examination (Visits 19, 25, 31, 37, 43, 49, and 55).

Table 7-3 Acceptable Time Window

Study Period (Study Visit)	Acceptable Time Window	Study Procedures
Screening Period	Before the day of enrollment	
 • DNA typing for HLA-A • Sample collection for antigen expression assessment • Height
	Within 28 days before the day of enrollment	
 • Physical examination • Weight • ECG • PS (ECOG) • Pregnancy test • Tumor evaluation (diagnostic imaging)
	Within 28 days before the day of enrollment and after 21 days from the last administration of chemotherapy	
 • Routine laboratory test (hematology, blood chemistry, and urinalysis, specified in Table 7-2)
Treatment Period (Visit 1)	Prior to initial administration	
 • Enrollment in the study • Physical examination • Vital signs • Sample collection for CTL analysis and repertoire analysis • QOL questionnaires
Treatment Period (Visit 2 to 18)	± 3 days	
 • Administration • Physical examination • PS (ECOG) • Vital signs
	± 7 days	
 • ECG • Sample collection for CTL analysis and repertoire analysis • Tumor evaluation (diagnostic imaging)

Study Period (Study Visit)	Acceptable Time Window	Study Procedures
		
 • Routine laboratory test (hematology, blood chemistry, and urinalysis, specified in Table 7-2) • QOL questionnaires
Treatment Period (Visit 19 to 58)	± 3 days	
 • Administration • Physical examination • PS (ECOG) • Vital signs
	± 7 days	
 • ECG • Routine laboratory test (hematology, blood chemistry, and urinalysis, specified in Table 7-2) • QOL questionnaires

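### The only pregnancy test before dosing may be up to 28 days old, contraception is required only from enrollment, and exclusion 18 names a test at enrollment that the schedule does not contain

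*Protocol*

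**What the plan says.** **Eligibility.** Protocol 4.3, exclusion 18, has two sentences. The first excludes "Female patients who are lactating or pregnant". The second adds: "Female patients who are of childbearing potential, not included in any of the following, are positive for the pregnancy test at enrollment". The synopsis has the same wording ("are positive for the pregnancy test at enrollment"). The lead-in to the list is "Patients who meet any of the following criteria by the end of screening period will be excluded from the study".

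**Contraception.** Exclusion 19, in 4.3 and in the synopsis, requires effective contraception "from enrollment to 90 days after completion or discontinuation of study treatment".

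**Schedule.** Section 7.4.6.2 states: "Urine or serum pregnancy test will be performed at screening in both the S-588410 and the Observation Groups". The next test is at Visit 59 or Discontinuation, for the S-588410 Group only. Table 7-3 (section 7.9) puts the screening pregnancy test in the row headed "Within 28 days before the day of enrollment". Its Visit 1 row, which covers what is done before the first administration, lists enrollment, physical examination, vital signs, blood samples and questionnaires, but no pregnancy test. Appendix 1 marks the test at screening (Day -28 to -1) and not at Visit 1 (Day 1).

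**The concern.** The criterion points to a test at one time and the schedule supplies it at another. The practical question is what protects a woman of childbearing potential between her screening test and her first injection. Under the schedule she may have tested negative early in screening, and until enrollment she is under no obligation to use contraception. If she conceives in that interval and does not know it, she could receive S-588410 with every scheduled step carried out as written.

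After that, no further test is scheduled until Week 104 or discontinuation. Dosing is weekly for 12 weeks and every two weeks thereafter. Section 7.6.10 stops the drug and triggers reporting, but only once the pregnancy is recognised.

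The stake is unrecognised fetal exposure. By section 1.3 the five-peptide combination had not itself been given to humans, although its component peptides had been evaluated in earlier clinical studies. The protocol evidently regards exposure as something to avoid: it excludes pregnancy, requires contraception until 90 days after treatment, and stops dosing if pregnancy occurs.

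**Working it through.** **Inputs**
- Screening days: -28 to -1; Visit 1 is Day 1; there is no Day 0 (Appendix 1).
- Window for the screening test: 28 days before enrollment (Table 7-3).
- Enrollment: a Visit 1 procedure, done before the first administration (Table 7-3).
- First dose: taken as Day 1. Table 7-3 implies this. So does section 8.9.1, which places the CTL baseline on the date of the first dose while the schedule draws that sample at Visit 1. Section 7.4.1 also has injection sites checked just before the Visit 2 injection, which presupposes an earlier one.
- Contraception starts at enrollment (exclusion 19).

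**Formula.** With no Day 0, a test on Day d (d < 0) has age 1 - d - 1 = -d days on Day 1.

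**The plan's own figure.** Test on Day -28: 1 + 28 - 1 = 28 days, which matches the 28-day window. Test on Day -1: 1 + 1 - 1 = 1 day. The days with no contraception requirement between test and enrollment are the same 1 to 28.

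**The readings side by side**

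| Reading | Test relied on | Age of test at first dose | Days from test to enrollment with no contraception requirement | Do criterion and schedule agree? |
|---|---|---|---|---|
| Schedule followed | Screening, Day -28 to -1 | 1 to 28 days | 1 to 28 | Only if *at enrollment* is read loosely |
| Criterion taken literally | Visit 1, before dosing | About 0 | About 0 | No: the test is not scheduled |
| Proposed (7-day example) | Screening, Day -7 to -1 | 1 to 7 days | 0 | Yes |

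In the last row the maximum age is 1 + 7 - 1 = 7 days. The maximum falls by 28 - 7 = 21 days, or 21/28 = 75%. That percentage depends wholly on choosing 7 days, which is an example and not a protocol figure.

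**Which reading is more natural?** The criterion refers to *the* pregnancy test, and only one exists before dosing. Exclusion criteria are judged by the end of screening. The protocol also uses the same phrase loosely elsewhere: section 7.2.1 asks for TNM classification "at enrollment in the study", as a baseline characteristic, and Appendix 1 collects those at screening. The screening test is therefore the likelier meaning.

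**Sensitivity to the first-dose day.** If the poorly rendered table in Appendix 1 were read as placing the first dose at Visit 2 (Day 8), a Day -28 test would be 8 + 28 - 1 = 35 days old. The interval without a contraception requirement would still be 1 to 28 days, because it ends at enrollment.

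**The case against.** The strongest defence has four parts.

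- **The wording is clear enough in context.** Only one test exists before dosing, and a site is unlikely to wonder which one counts. This largely stands, and it is why the schedule-based reading is treated as the main one. It does not remove the interval; it is the reading that creates it.
- **A 28-day window is the protocol's standard.** The lymphocyte, laboratory and eosinophil criteria use it, as do ECG, performance status and imaging. This stands as far as it goes: the window is consistent and contradicts nothing, and the protocol sets no limit on how recent a pregnancy test must be. Shortening it is an improvement, not the correction of a miscalculation.
- **Other safeguards exist.** Known pregnancy is excluded outright. There is a physical examination at Visit 1 before dosing. Exclusion 19 is assessed before entry, so contraception has to be discussed during screening, and exclusion 22 leaves the investigator discretion. All this lowers the risk. None of it requires contraception before enrollment or a repeat test.
- **The numbers are tiny.** Exposure would need an early test, conception in the interval and failure to recognise it, among what are probably very few women. This stands and limits the weight of the point.

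A reader might infer that the gap of up to 28 days exists however exclusion 18 is read. The documents do not support that. Enrollment is a Visit 1 step before the first administration, so a site that takes the criterion literally would test then and have almost no gap. On that branch only the mismatch between criterion and schedule is left.

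**Conclusion.** The point holds as a small patient-safety and wording matter. Followed as scheduled, the protocol permits, but does not force, a first dose on a pregnancy test 1 to 28 days old, with no contraception requirement since that test. Taken literally, exclusion 18 calls for a test that is not in the schedule. One of the two texts needs repair on either reading.

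The day count assumes that enrollment and first dose both fall on Day 1. Only women of childbearing potential among the planned 42 S-588410 patients are at risk of exposure. The protocol does not give their share; that it is small is an assumption. It would be wrong to infer a number of exposed pregnancies, or that women known to be pregnant could be dosed. Nothing in the documents supports the former, and the first sentence of exclusion 18 prevents the latter. No endpoint, sample size or analysis is affected. This is a cheap improvement to have, not a condition for the trial's validity.

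**What to change.** In one amendment:

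1. **Table 7-3:** give the screening pregnancy test its own row with a short window before enrollment, for example Day -7 to -1. The table already gives routine laboratory tests a separate screening window, so the format exists.
2. **Exclusion 18, in 4.3 and the synopsis:** name that test and window, for example *positive urine or serum pregnancy test within 7 days before enrollment*.
3. **Exclusion 19, in 4.3 and the synopsis:** start contraception for women of childbearing potential at consent or at the screening test. The end of the period stays as it is.

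Apply this to every screened woman of childbearing potential. Group assignment depends on an HLA-A result that may still be pending during screening, so a single rule avoids separate wording by group or by HLA status. The test still falls in screening, so the lead-in to 4.3, section 7.4.6.2 and the screening marks in Appendices 1 and 2 remain true. The pregnancy-test footnotes there can carry the window if wanted.

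The cost is wording in five places, and for a few women a test timed later or one urine test repeated. That includes some who turn out to belong to the untreated Observation Group and gain nothing from the shorter window.
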